#### Exclusion criteria for age matched controls

- Major congenital or chromosomal anomalies
- Inability to tolerate enteral nutrition/ regular cow's milk, breast milk or soy formula

- History of liver/intestinal transplantation
- Active milk protein allergy
- Inflammatory bowel disease
- Multiorgan failure

Inclusion Criteria for glutamine and placebo group of SBS patients (n=36; 18 per site)

- Males and females  $\leq$  12 months of age (corrected for gestational age)
- Patients who have undergone small bowel resection due to complications of or related to NEC, omphalocele, gastroschisis or intestinal atresia with known small bowel length
- Patients who have been PN dependent for more than 42 consecutive days (6 weeks) and currently on TPN at time of enrollment. This would include patients who were off TPN for  $<$  7 consecutive days.
- Patients who have the ability to take partial enteral nutrition of at least 5ml/hr breast milk or elemental formula (Elecare® is the preferred formula at both clinical sites but use of other elemental formula does not exclude the patient) (via gastric or intestinal tube, or orally) to allow the appropriate dose of GLN (0.6 g/kg/day) or placebo (L-alanine)
- Signed informed consent for the use of GLN or placebo obtained

Exclusion Criteria for glutamine and placebo group of SBS patients

- Major congenital or chromosomal anomalies
- Inability to tolerate enteral nutrition that will preclude treatment with enteral GLN or L-alanine placebo for  $>$ 2 consecutive weeks
- Liver/intestinal transplantation
- Multiorgan failure

B. Withdrawal Criteria

1. Patient cannot complete evaluation visit assessments
2. Patient develops any of the exclusion criteria detailed above
3. Patient develops significant hepatic dysfunction (defined as INR  $>$  2.5 or direct serum bilirubin level  $>$  10 mg/dL)
4. Parent(s)/legal guardian are unwilling to administer the GLN or placebo at the required dosage
5. Patient is lost to follow-up
6. Patient has 3 missed study visits
7. It is in the patients best interest

C. Dropouts

Data collected from patients who voluntarily withdraw from the study or who are withdrawn from the study will be included in the final analysis using intent to treat. Patient and control enrollment will continue until 32 patients complete all requested study requirements outlined. The reason for withdrawal will be documented.

D. Stopping Rules

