#### F. Evaluating compliance

All of the subjects will be instructed to bring to the monthly visits, the containers containing the supplement supplied at the previous visit. The study team will count the remaining bags left over. We will also evaluate the diary provided to the families. Compliance will be evaluated based on the diary and the number of returned containers. Families are expected to be 90% compliant. If the child/family is less than 90% compliant, the family will receive additional counseling to identify reasons and how to attain this level of compliance. Children will remain in the study as long as they receive at least 70% of the expected amount for 3 consecutive months. The level of compliance on enteral GLN effect will be included in the analysis. Children who receive less than 70% or more than 120% of the prescribed glutamine or placebo will be considered to be non-compliant. The reason for non-compliance will be documented and included in the final analysis. Average intake/day of glutamine by the patients will be included in the analysis including the response based on dose received.

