## **X. Assessment of Efficacy**

**Hypothesis 1:** Enteral GLN supplementation in infants with SBS after massive bowel resection for NEC will decrease BSI, and thereby decrease systemic proinflammatory cytokine concentrations.

**Specific Aim 1:** To perform a double-blind, randomized, placebo controlled, 6-months pilot study of enteral GLN (0.6g/kg) vs. isocaloric, isonitrogenous alanine (placebo) treatment in PN-dependent SBS children due to NEC to evaluate the efficacy of GLN to decrease: a) BSI (primary endpoint) and b) serial serum concentrations of TNF- $\alpha$ , IL-1 $\beta$ , IL-6 and IL-8 (secondary endpoint). **The primary outcome is the incidence of BSI during the 6 months on GLN supplementation.** BSI is defined as laboratory-confirmed, culture-proven bloodstream infections that meet the Centers for Disease Control and Prevention (CDC) definition. This allows for the distinction between catheter related-BSI and other causes of BSI.

**Secondary outcomes:** 1) Plasma proinflammatory cytokine levels (TNF- $\alpha$ , IL-1 $\beta$ , IL-6, IL-8); 2) readmissions and hospital length of stay; 3) proportion of nutrition delivered enterally versus parenterally; 4) stool sIgA levels; 5) Plasma glutamine.

**Expected results:** We expect that the SBS children on enteral GLN supplementation will have significantly fewer BSI and greater decline in blood cytokine levels during the period of therapy.

**Hypothesis 2:** Enteral GLN supplementation will improve somatic growth parameters in Aim 1 patients.

**Specific Aim 2:** To assess the efficacy of 6 months of therapy with enteral GLN on somatic growth parameters [length velocity (primary endpoint), weight velocity, mid arm circumference and head circumference] in Aim 1 subjects and the impact of BSI on these growth parameters.

**The primary outcome for specific aim #2 is length velocity.** Secondary outcomes are growth parameters of weight mid arm circumference and head circumference velocities. These are clinically relevant growth parameters identified by our preliminary data in which SBS children had growth delay with short lengths and smaller head circumferences than infants without NEC or SBS.

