### **XIII. Statistical Analysis Plan**

To assess the comparability of the two treatment groups, demographic and baseline data will be summarized for each treatment group. For continuous data, mean, standard deviation, median, min, max, first quartile and third quartile will be presented. Comparisons will be made using the two-independent sample t-test or the Wilcoxon Rank sum test, depending on the distribution of the variable. For categorical data, frequencies and percentages in each group will be presented. Comparisons will be made using Fisher's exact test. These tests will be conducted at the two-sided, 5% level of significance. In addition, demographic and baseline data for the control group will be summarized and presented as described above. The statistical analysis plan for each aim is presented below.

**Aim 1 Hypothesis:** Enteral GLN supplementation in infants with SBS after massive bowel resection for NEC will decrease BSI, and thereby decrease systemic proinflammatory cytokine concentrations.

The primary outcome variable is the incidence of BSI during the 6 months on GLN supplementation. BSI is defined as laboratory-confirmed, culture-proven bloodstream infections that meet the Centers for Disease Control and Prevention (CDC) definition. To compare the incidence of BSI during the 6 month time period, the percent of patients with at least one BSI will be calculated in each group. Since this is a pilot study, the desire is to detect a trend in improvement of BSI with GLN supplementation. Therefore the 2 groups will be compared using the Fisher's Exact test at the one-sided 10% level of significance which will indicate a significant trend. As an additional analysis, time to first BSI will be displayed using Kaplan-Meier (K-M) curves. The log-rank test will be used to test for differences in curves between treatment groups. Patients will be censored if they exit the study prior to having their first BSI. As a further exploratory analysis, time to multiple-event analyses techniques will be used to compare groups where the multiple events represent multiple episodes of BSI within patients.

Secondary outcomes include the following and will be tested at the two-sided 5% level of significance:

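### The plan does not say how an infant who leaves without a BSI counts in the primary Fisher test, and no study procedure collects BSI after withdrawal

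*Combined protocol and SAP*

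**What the plan says.** **Measure and test.** Section XIII (Aim 1) computes "the percent of patients with at least one BSI will be calculated in each group" and compares the groups by Fisher's exact test at one-sided 10%. It gives no denominator.

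**Analysis principle.** Section IX.C (Dropouts) says that data from withdrawn infants "will be included in the final analysis using intent to treat". The same section enrols until 32 infants complete, and the sample size text is built on 16 completers per group.

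**Infants who leave BSI-free.** The one rule is "Patients will be censored if they exit the study prior to having their first BSI". It follows the log-rank sentence in Section XIII and serves that additional analysis.

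**Routes out of the study.** Section IX.B lists parents being "unwilling to administer the GLN or placebo at the required dosage" and also "Patient develops any of the exclusion criteria detailed above". Section IX.F adds: "Children will remain in the study as long as they receive at least 70% of the expected amount for 3 consecutive months".

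**Wording of the outcome.** Section X has "The primary outcome is the incidence of BSI during the 6 months on GLN supplementation", and Section XIII repeats it almost word for word. The analysis sentence that follows in Section XIII refers only to a six-month period, with no treatment condition.

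**The concern.** Intent to treat settles that withdrawn infants are included. It does not settle what is entered for an infant whose BSI-free record stops early. A 2x2 table cannot use censoring, so such an infant must be left out, scored as no BSI, or scored as BSI. The completer-based sample size suggests the first; Section IX.C suggests one of the others.

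The missing data are also partly created by the design. Refusal of product is a reason for withdrawal, and low intake puts continued participation at risk. BSI history is taken at study visits. Other possible sources do not clearly reach withdrawn infants:

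- Data extraction (Section IX.I) is not tied to them.
- The monthly tracking in Section IX.D is a clinical process and covers catheter-associated BSI only.
- The 30-day follow-up in Section XII is for adverse events, and BSI is normally not reported as one.

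At stake are the trend decision and the BSI rates that are meant to inform the definitive trial. Scoring leavers as no BSI favours whichever arm loses more infants.

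**Working it through.** **Inputs from the documents.** 18 enrolled and 16 completing per arm; 10% dropout; BSI rates of 75% versus 30%; Fisher's exact test at one-sided 10%.

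**Assumptions.** Constant BSI hazard; exit times uniform over 180 days and unrelated to BSI, except where stated. Withdrawal rates other than 10% and the 45% rate are illustrative. Pairs such as 10/20 mean percent withdrawal on placebo/GLN.

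**1. The plan's own figure.** Enumerating all tables for 16 per arm at 75% versus 30%, and rejecting when one-sided p is at most 0.10, gives 85.7%. The stated power of at least 85% reproduces.

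**2. Expected BSI-free leavers.** With six-month risk p, the chance of being BSI-free at a uniform exit time is the integral of (1-p)^u over u from 0 to 1, which is p / (-ln(1-p)).

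- p = 0.75: 0.75/1.386 = 0.541.
- p = 0.30: 0.30/0.357 = 0.841.

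Each arm loses 18 x 0.10 = 1.8 infants, 3.6 in all. BSI-free leavers: 1.8 x 0.541 + 1.8 x 0.841 = 2.5 at 75% versus 30%, and 2 x 1.8 x 0.541 = 1.9 at 75% in both arms.

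**3. Observed risk with leavers scored as no BSI.** With withdrawal proportion w, observed risk = (1-w)p + w[1 - p/(-ln(1-p))]. For p = 0.75:

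- w = 10%: 0.675 + 0.046 = 0.721.
- w = 20%: 0.600 + 0.092 = 0.692.
- w = 30%: 0.525 + 0.138 = 0.663.

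For p = 0.30 and w = 10%: 0.270 + 0.016 = 0.286.

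**4. Power at equal 10% withdrawal.** The completers' figure averages exact power over the binomial number of completers in each arm.

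| Handling | 75% v 30% | 75% v 45% |
|---|---|---|
| Completers only | 85.0% | 55.5% |
| Leavers = no BSI, 18 per arm | 88.9% | 60.9% |
| All followed, 18 per arm | 90.8% | 63.2% |

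**5. False positives, 75% in both arms, leavers = no BSI, 18 per arm.**

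| Withdrawal, placebo/GLN | False positives |
|---|---|
| 10/10 | 5.1% |
| 10/20 | 7.6% |
| 10/25 | 9.1% |
| 10/30 | 10.9% |

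With everyone followed the figure is about 5%, whatever the withdrawal.

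**6. Does the rule change decisions?** In 20,000 simulated trials per case at equal 10% withdrawal, completers-only and leavers = no BSI disagree in about 3% of trials (75% v 75%), 6% (75% v 30%) and 12% (75% v 45%). One chosen example has 1 placebo and 3 GLN infants leaving BSI-free. Left out, 12/17 v 7/15 gives p = 0.155. Scored as no BSI, 12/18 v 7/18 gives p = 0.091. The 10% line is crossed by the rule alone.

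**The case against.** The best defence is that little goes wrong under the plan's own assumption. With 10% withdrawal in both arms, false positives are about half the nominal 10%, and power at 75% versus 30% is 85% or more under each handling in the table. That stands. A reader might infer that the missing rule inflates the error rate of the trial as planned; it does not. Passing 10% with unrelated exits takes roughly threefold withdrawal on GLN. The documents give thin grounds to expect that: Section VI lists more symptoms for GLN (nausea 22%, against nausea and vomiting 11% for alanine), while Section III reports good tolerance in infants.

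A reader might also infer that stopping product always ends BSI recording. Section IX.H withholds product in certain complications while the infant is still enrolled. Section XII discontinues it for some related reactions, which Section IX.B does not list as a reason for withdrawal. The link holds for refusal and for low intake, not for every stop.

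A third tempting reading is that "The primary outcome variable is the incidence of BSI during the 6 months on GLN supplementation" fixes an on-treatment analysis. Placebo infants are never on GLN, and the analysis sentence drops the condition. The phrase is an ambiguity to reconcile and no more.

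Finally, a reader might suppose that infants heading for infection leave first, so that false positives rise far above 10%. They would be higher in that case, but the size depends on timing. If such infants are twice as likely to leave but exit times stay uniform, the figures are 8.1% at 10/20 and 12.0% at 10/30. If every leaver who would have had a BSI exits before it, they are 13.7% and 27.0% even with no such link. No passage supports that timing, and an infant withdrawn for a complication of infection may already have a recorded BSI.

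The planned log-rank analysis handles exits unrelated to BSI. It is an additional analysis with no stated level, and it does not determine the Fisher result.

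**Conclusion.** The gap is real and concerns the primary endpoint. The plan promises intent to treat, sets no score for an infant who leaves BSI-free, and has no procedure for obtaining the missing outcome. At the planned equal 10% dropout the effect is modest: no inflation of false positives, up to about 6 points of power at 75% versus 30% (85.0% to 90.8%), and a different decision in about 3 to 12% of trials. The harm under unequal withdrawal (7.6% at 10/20, 10.9% at 10/30) rests on assumed rates, constant hazard, uniform unrelated exits, and leavers scored as no BSI. The sample size and its stated power are correct. This is a cheap improvement to make before unblinding, and not a flaw that undermines the pilot.

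**What to change.** 1. **Keep recording the outcome.** Separate stopping product from leaving the study for the purpose of outcome recording. Record BSI to day 180 for every randomised infant whose family agrees, by chart review at both sites plus the monthly tracking in Section IX.D. That tracking covers catheter-associated BSI only, so other BSI must come from the chart. No change to when product is stopped is proposed.
2. **State the primary analysis.** Use all randomised infants as assigned, for BSI in the 180 days after randomisation. Align the outcome wording in Sections X and XIII with this, and say how an infant randomised but replaced before the first dose (Section IX.G) is counted.
3. **State one rule for status that stays unknown.** Add two sensitivity analyses: completers only, and a worst case with unknown = BSI on GLN and no BSI on placebo.

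**Cost.** SAP wording, family agreement to continued record review, and a chart check for about 2 to 4 infants.

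**Downside.** Counting BSI after product stops dilutes the effect of taking GLN. Suppose 10% of GLN infants stop at a uniform time and return to the placebo hazard. Risk among stoppers is 1 - (0.70 - 0.25)/(1.386 - 0.357) = 0.563, so the GLN risk becomes 0.9 x 0.30 + 0.1 x 0.563 = 0.326. Power at 18 per arm then falls from 90.8% to 87.5%.

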### **Sample size**

This is a pilot study and will provide estimates of effect sizes and variability to be used to power a future definitive study. The power of this pilot study was investigated based on the primary endpoint of BSI infection rate and the study was powered to detect a trend toward improvement in BSI rates. For this study, we defined “trend” as a significant improvement tested at the one-sided, 10% level of significance. A total of 18 patients per treatment group will be enrolled in the study. Assuming a 10% dropout rate, it is expected that 16 patients per treatment group will complete the study. A sample size of 16 patients per treatment group will provide at least 85% power to detect a trend if the true BSI rates are 75% versus 30% BSI rate at the one-sided 10% level of significance. This calculation is based on the Fisher’s exact test for two proportions.

A sample size of 16 patients per treatment group will also provide at least 80% power to detect a geometric mean ratio of 2.0 for the two treatment groups for the proinflammatory cytokines assuming a coefficient of variation of 0.7 using a two-sided, 5% level of significance test.

We anticipate applying for a follow up R01 /U01 to attract other centers that will allow a larger more definitive study regarding the use of GLN in pediatric SBS.

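### Fisher's exact test is valid here and the stated power is right, but it uses little more than half of the 10% error the pilot accepts; Boschloo's exact test would recover some power at almost no cost

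*Combined protocol and SAP*

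**What the plan says.** In section XIII (Statistical Analysis Plan, Aim 1) the primary outcome is reduced to a yes/no result per infant over six months: "the percent of patients with at least one BSI will be calculated in each group". The test follows, a Fisher's "Exact test at the one-sided 10% level of significance which will indicate a significant trend". The Sample size subsection defines a trend as "a significant improvement tested at the one-sided, 10% level of significance".

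On numbers, that subsection says "A total of 18 patients per treatment group will be enrolled in the study" and, after 10% dropout, "it is expected that 16 patients per treatment group will complete the study". Sixteen per arm "will provide at least 85% power to detect a trend" when the true rates are 75% and 30%, and the calculation is said to rest on Fisher's exact test. Section IX.C (Dropouts) keeps withdrawn infants in an intent-to-treat analysis, so the number analysed could be nearer 18 per arm. The plan does not state the attained level of the test and names no less conservative exact alternative.

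**The concern.** The one-sided 10% threshold is a deliberate choice: because this is a pilot, the plan accepts more false positives than usual in return for a better chance of seeing a trend. Fisher's test conditions on the total number of infected infants. With 16 per arm, only a few p-values are possible for each total, and the largest one that does not exceed 0.10 is often well below it. The plan may therefore pay for a tolerance of 10% and receive much less.

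At stake is the chance of missing a trend in a small trial in a rare condition, when the result is meant to inform a larger study.

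**Working it through.** **Inputs.** Arms of 16 (expected completers) up to 18 (enrolled); one-sided threshold 0.10; planning rates 75% and 30% (Sample size); 1:1 allocation in blocks by site and colon status (section IX.H). Dropout: 18 × 0.90 = 16.2, so 16 per arm.

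**Formulas.** Let x be the infected infants among n on placebo and y those among m on glutamine, with t = x + y.
- Fisher p(x, y) = sum over k ≥ x of C(n,k)·C(m,t−k)/C(n+m,t).
- Fisher's test rejects if p ≤ 0.10.
- True level = maximum over a common rate π of the sum of Bin(x; n, π)·Bin(y; m, π) over all rejected tables.
- Power = the same sum with 0.75 for placebo and 0.30 for glutamine.
- Boschloo's test rejects if Fisher p ≤ c, where c is the largest cut-off that keeps the true level at or below 10%.

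**The plan's own figure.** Enumerating all 17 × 17 tables at 16 per arm gives Fisher power of 85.7% at 75% v 30%. The statement of at least 85% is confirmed.

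**True level at 16 per arm.** Fisher: 4.6% at a common rate of 30%, 5.5% at 50% (the maximum) and 4.4% at 75%. The unused share is (10 − 5.5)/10 = 45%. Boschloo: c = 0.1426, maximum level 9.5%.

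**Why the gap arises: one example.** Take 20 infected in total, 16 per arm; C(32,20) = 225,792,840.
- P(x ≥ 13) = (6,406,400 + 960,960 + 69,888 + 1,820)/225,792,840 = 7,439,068/225,792,840 = 3.3%.
- P(x = 12) = 1,820 × 12,870/225,792,840 = 10.4%.
- P(x ≥ 12) = 13.7%.

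At this total Fisher's test can work at 3.3% or 13.7% and nothing between, so it takes 3.3%. A result of 12/16 v 8/16 has Fisher p = 0.137: no trend by Fisher, a trend by Boschloo.

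**Power at the planned 75% v 30%** (gains from unrounded values):

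| Placebo/GLN | Fisher max level | Boschloo max level | Fisher power | Boschloo power | Gain (points) |
|---|---|---|---|---|---|
| 16/16 | 5.5% | 9.5% | 85.7% | 90.7% | 5.0 |
| 17/16 | 5.7% | 9.1% | 84.0% | 90.9% | 6.9 |
| 16/17 | 5.7% | 9.1% | 84.8% | 90.7% | 5.9 |
| 17/17 | 6.1% | 9.7% | 88.5% | 91.4% | 2.8 |
| 17/18 | 5.1% | 9.2% | 86.3% | 92.5% | 6.3 |
| 18/17 | 5.1% | 9.2% | 86.4% | 92.7% | 6.3 |
| 18/18 | 6.6% | 10.0% | 90.8% | 92.3% | 1.5 |

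In every row Boschloo's rejection region contains Fisher's.

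**Smaller effects (assumed here, not in the plan).**
- 75% v 40%, 16 per arm: 67.0% v 76.9%, gain 9.9 points.
- 75% v 50%, 16 per arm: 43.4% v 56.7%, gain 13.2 points.
- 75% v 50%, 18 per arm: 50.6% v 60.7%, gain 10.0 points.

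**Other candidates at 16 per arm.** Fisher mid-p has a maximum level of 10.8%, above the stated limit. The Z-pooled unconditional test stays within it (7.3%) but gains only 0.6 points at 75% v 30%.

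**The case against.** Nothing in the plan is wrong. A significance level is a ceiling on false positives, and Fisher's test respects it. The power was computed for Fisher's test, so the conservatism is already counted. All of this stands.

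A reader might infer from the 5.5% that the trial misstates its error rate, that its power is overstated, or that it has too few infants. The documents support none of these: the threshold is a nominal limit, and 85.7% meets the claim. The two rows below 85% (17/16 and 16/17) do not contradict a statement made for 16 per arm.

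A reader might also take 13 points as the general loss. That figure needs 75% v 50%, which the plan nowhere assumes. If intent to treat keeps 18 infants in each arm, the gain at the planned rates is only 1.5 points. The gain also belongs to Boschloo's test in particular.

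The best remaining argument is a preference for conditional control. Fisher's test holds error at or below 10% for every total number of infected infants; Boschloo's holds it over the whole sampling distribution. In the 12/16 v 8/16 example, rejection carries a conditional error of 13.7%. This is a real but small downside. The plan claims no conditional guarantee, and the downside can be handled by disclosure.

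Finally, the pilot's effect estimates are the same under either test, and the plan adds a log-rank test and multiple-event analyses. That limits the consequence but is no reason to refuse a free gain on the primary test.

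**Conclusion.** The point holds as an efficiency improvement. Fisher's test is valid at a one-sided 10% threshold and the stated power is correct at 16 per arm, but the true level is at most 5.5% there, and at most 5.1% to 6.6% over equal or one-apart arms of 16 to 18. A large part of the error that the pilot deliberately accepts is left unused.

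Against Boschloo's test at the planned rates, the cost is 5.0 points of power at 16 per arm, 1.5 at 18 and about 6 to 7 when the arms differ by one. It reaches 10 to 13 points only under assumed smaller effects such as 75% v 40–50%. The figures rest on independent binary outcomes, the 75% placebo rate, and the arm sizes that the analysis set finally yields.

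**What to change.** Before unblinding, so that the change cannot look data-driven:

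1. In section XIII (Aim 1) and the Sample size subsection, replace Fisher's exact test by Boschloo's unconditional exact test at the one-sided 10% level, with the direction stated as fewer infants with BSI on glutamine.
2. Restate power for 75% v 30% as about 90% with 16 per arm.
3. State that error is controlled over the sampling distribution and not conditionally on the total infected, so that some declared trends will have a Fisher p between 0.10 and about 0.15. Report the Fisher p-value alongside.
4. Do not substitute plain mid-p, whose level can exceed 10%.

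The cost is a few sentences in the analysis plan. The test is available in standard software (scipy, for example). No infants, visits or data are added, and in the arm sizes checked no result that Fisher's test would call a trend is lost.
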